Each subject folder will be stored in a locking file cabinet inside the primary investigators locking office located at the Split Medical School until [name] travels back to the United States. Subsequently, all hard copy data will be scanned into electronic format while in Croatia and saved on a password protected and fingerprint protected locked hard drive and hand carried by [name] back to the United States. All hard copies will be left with collaborator [name], who will store these hard copies indefinitely. All hard copies generated in the US will be kept in the Cardiopulmonary and Respiratory Physiology Lab in locked filing cabinets inside of a locked laboratory. These electronic format data will subsequently stored inside the primary investigators locking office located at the University of Oregon Cardiopulmonary and Respiratory Physiology Lab. The de-identified data will be kept for at least 7 years after publication, per NIH guidelines. In the unlikely event the data are not published, they will be kept for at least 10 years after collection. This will ensure sufficient time for publication after data have been collected considering some trainees take up to 6 years to graduate, and often publication does not occur until many years after graduation.

Each subject will be assigned an ID using a random number code system consisting of three to five letters describing the study (e.g., APNEA or SCUBA) and a random, non-repeating number (1-1000). This ID

will be associated with their unique folder, which will contain all study documents and data collected including all associated forms (i.e. informed consent document).

The primary investigator will maintain a subject ID key capable of identifying subject IDs to subject names and contact information to provide us with the ability to identify subjects as additional questions or research findings arise. This ID key will be kept in a locked filing cabinet also within the office of the primary investigator. No contact information will be stored with subject data.

De-identified data may potentially be shared with other investigators for research purposes.

G. Potential Research Risks or Discomforts to Participants

Confidentiality:

If data is lost or stolen, subjects could experience invasion of privacy. To minimize the potential invasion of privacy, we are not collecting social security numbers so that the potential economic impact is greatly minimized. All of our files will be kept in a locked filing cabinet to prevent theft and data will be de-identified. Data acquired on computers will be password protected. As such, the probability of the adverse outcomes discussed above is low, and the severity is minimal.

Psychological:

Male subjects will be asked to go shirtless for all echocardiography and exercise studies. Female subjects will need to wear a sports bra for all echocardiography and exercise studies. Female subjects will be allowed to wear a loose fitting scrub top (provided by the researchers) over their sports bra that allows for echocardiographic imaging and EKG electrode placement. Accordingly, both male and female subjects could potentially feel embarrassed or have modesty issues by being shirtless (males) or when only wearing a sports bra (females). To minimize the risk of embarrassment or modesty issues, both male and female subjects will be allowed to wear a loose fitting scrub top (provided by the researchers) that allows for concealment of upper body but also allows for echocardiographic imaging and EKG electrode placement. Female subjects will still be allowed to wear the sports bra with the scrub top which will allow for required instrumentation, but will also allow the subject to cover up as much as possible for the study. Both males and females may wear sweat pants or shorts, i.e. whatever makes the subject comfortable. As such, the probability of the adverse outcomes discussed above is low, and the severity is minimal.

Physiological:

Pulmonary Function Tests: Risks associated with pulmonary function testing include shortness of breath, cough, dizziness, and possible loss of consciousness. To minimize risks, the co-investigators will administer all pulmonary function tests and allow subjects to rest between measurements. Lung function testing performed in our lab is routinely and repeatedly done and performed in pulmonary function labs all over the world according to American Thoracic Society and European Respiratory Society standards. These tests can be stopped at anytime if cough, dizziness, shortness of breath, or possible loss of consciousness occurs. Co-investigators will be monitoring the subjects for any signs of discomfort. The probability and severity of these risks is very low. These tests can be stopped at anytime if cough, dizziness, shortness of breath, or possible loss of consciousness occur. Co-investigators will be monitoring the subjects for any signs of discomfort.

Intravenous catheter: Risks associated with placement of an intravenous catheter (IV) include pain and/or bleeding during placement, vasovagal syncope, hematoma (pooling of blood under the skin), infection, and vessel blockage. The placement of the IV may cause some discomfort with rare bleeding or bruising at the puncture site. It also carries the risk of infection. To mitigate risks associated with vasovagal syncope, the subject will be safely positioned upright and sitting in an IV chair, and the subject will be continually monitored by [name] and/or a member of the research team. [name] or trained member of the research team will place IVs. We use aseptic techniques, sterile needles and IV catheters, so the probability

of experiencing any severe side effects such as infection is low and is not different from the risks of an IV being placed for the purpose of drawing blood for a routine clinical test. Some individuals may also feel like fainting at the site of needles of blood (vasovagal response). As such, the **probability** of the adverse reactions discussed above is low, and the **severity** is minimal.

Blood Removal: Risks associated with the removal of blood include an aversion to seeing blood that could result in nausea, vasovagal syncope, increased stress, and/or feeling faint. To mitigate these potential risks, the subject is continually monitored by [name] PhD and colleagues during IV placement. In addition, the subject is safely and comfortably positioned on either a gurney or IV chair. In this way, the potential risk of vasovagal syncope (i.e., fainting) is mitigated. As such, the **probability** of the adverse reactions discussed above is low, and the **severity** is minimal.

Saline Contrast Echocardiography: The PI has been using saline contrast echocardiography since 2003 to detect blood flow through intracardiac and intrapulmonary shunts. Risks: transient dizziness associated with agitated sterile saline injection in patients with cardiac shunting. With respect to exercise, the Principal Investigator has >10 years of experience using TTSCE in a research setting. In 4 years (2003-2007) at the University of Wisconsin Madison, approximately 60 human (male and female) subjects (including 8 subjects with a patent foramen ovale) were tested without a single adverse event related to TTSCE. Additionally, research done at the University of Oregon between 2008 and 2019 has involved >200 subjects using TTSCE at rest and during exercise without incident related to the TTSCE. We will use agitated sterile saline without preservatives. Furthermore, we will use a minimal volume (3-5 mL) of sterile saline. [name] or a trained member of the research team will perform saline contrast injections, while a trained and licensed ultrasonographer will perform echocardiography. The ultrasonographer will inspect the ultrasound machine for proper and safe functioning prior to use, and will identify any indications that the ultrasound machine may be functioning abnormally. In the event of such identification, repair and non-routine maintenance will be performed by a representative of the ultrasound manufacturer. Routine maintenance will be performed as needed by the ultrasound technician.

Mixed saline (saltwater), either alone or with 5% sugar in water **has been used to help see the ultrasound pictures (echocardiogram) for over thirty years.** Saline contrast bubble injections are routinely used to screen for the presence of a patent foramen ovale in the clinic. The American Society of Echocardiography Guidelines (2014) state that "...life threatening reactions are rare (<1 in 10,000)" when using contrast injections (including bubbles with protein shells) and The European Association of Echocardiography (2009) has stated that "... the evidence shows that contrast echocardiography is very safe in clinical practice." And this includes using stabilized bubbles with protein shells and we only use non-stabilized saline contrast bubbles in our lab. We only use a small amount of air mixed with saline, thus the **probability** of any **severe adverse reaction** is very low. Given the evidence presented above, the **probability** of the adverse reactions discussed above is low. Although the **severity** of arterial gas emboli is high, given the amount of air used and the short life span of intravascular bubbles of this size, the likelihood of the constellation of unfortunate events required for a serious adverse reaction to occur is very small.

Breathing low oxygen (hypoxia) and high carbon dioxide (hypercapnia): Risks associated with exposure to hypoxia or hypercapnia during rest include headache, nausea, fatigue, dizziness and shortness of breath and the remote possibility of central nervous system impairment, insomnia, pulmonary and cerebral edema, and death. Subjects will be monitored with an electrocardiogram and peripheral estimate of arterial oxygen saturation using a forehead monitor. Exposure to hypoxia at rest will be brief to minimize the impact of low oxygen. The principal investigator has extensive experience conducting exercise tests with subjects breathing hypoxic gas mixtures in a research setting (Amann, Eldridge et al., 2006; Romer, Havercamp et al., 2007; [name] 2007; [name], Romer, et al., 2008; [name] et al., 2011; Laurie et al., 2010; Elliott et al., 2015). Although the severity of risks breathing hypoxic and hypercapnic gas is potentially high, given the

short duration of exposure and careful monitoring by the research team, the likelihood of a serious adverse event to occur is very small.

Risks associated with core temperature pill: The risks of using the temperature pills include mechanical injury to the mucus membranes if adequate care is not used. Risks of the temperature pill will be minimized by explaining the procedures to the volunteers. Additionally, ample lubricant (suppository) or water (oral) will be provided to the volunteer. Volunteers with history of obstructive diseases of the gastrointestinal tract including diverticulosis, diverticulitis, inflammatory bowel disease, peptic ulcer disease, Crohn's disease, ulcerative colitis, or previous GI surgery will not use a telemetric pill. These risks only apply to subjects in the SCUBA arm.

Risks for subjects undergoing SCUBA diving: During the research, examinees will dive once to a max depth of 30 meters. Dive time will be a max of 75 minutes. At 30 meters (100 feet), the maximum bottom time before decompression limits are reached is 20 minutes (PADI dive table). When decompression limits are reached or exceeded, a decompression stop on the reascent is needed. Divers can safely exceed recreational decompression limits by adding a decompression stop, as decompression stops are designed to greatly minimize the risks of decompression sickness. Dive computers will be used so subjects can monitor how long they can stay at their current depth before requiring a decompression stop and determine length of a required decompression stop (standardized diving protocol determined by diving computer Galileo, Uwatec). The dive will be done in the presence of a safety diver, a paramedics doctor, while the doctors working at the Institute for hyperbaric medicine will be thoroughly informed about the diving protocol and schedule. Divers will utilize SCUBA equipment owned and maintained by the Croatian Navy. During the dive, the following adverse events are possible:

1. Decompression sickness – a condition in which air bubbles dissolved in tissues suddenly become released into bloodstream due to the decrease of the ambient pressure. Common symptoms include pain in the joints, extremities, dizziness, nausea, vomiting, extreme tiredness, paralysis, collapse and fainting. The incidence of decompression sickness among divers is generally low, ranging from 0.013% to 1.25%. Decompression sickness is primarily related to the depth and duration of the dive, as well as to the duration of decompression while resurfacing.
2. Arterial gas embolization – the bubbles can reach arterial system in people with defects in the interatrial wall of the heart.
3. Embolization – during the quick decompression, bubbles of oxygen can move from tissues into circulation.
4. Expansion lung injury and pneumomediastinum – can happen during the breath hold while resurfacing.
5. Oxygen narcosis – as a result of toxic effects of high oxygen pressure on nerve conducting, symptoms comparable to drunkenness may happen.
6. Oxygen toxicity – toxic effects of oxygen can be caused by the high quantity of absorbed oxygen, and can present as burning sensations in lungs, spasms, dizziness and vomiting.

Because we will be working with experienced divers utilizing equipment owned and maintained by the Croatian Navy, the probability of these risks is very low, although the severity is moderate.

Sildenafil (Viagra): Adverse reactions previously observed in individuals taking Sildenafil include moderate hypotension, light headedness, dizziness, priapism, sensitivity to light and potential visual disturbances. These reactions are extremely rare and largely associated with individuals who are using Sildenafil for the management of erectile dysfunction or pulmonary artery hypertension. We will further minimize these risks by using healthy subjects with no previous history of cardiovascular disease and use a standard clinical dose of 50 mg P.O. We will also exclude subjects from participation during Stage #1 if they report currently taking specific contraindicated medications (outlined in the exclusion criteria in Table 1). [name], MD, Dr.

[name], and colleagues will be monitoring the subjects and ensuring the subject is not suffering from any negative side effects. Thus, the probability and severity of these risks is very low.

Safety Equipment available in the Laboratory of [name] in the department of integrative physiology at the University of Split School of Medicine in Split Croatia (where testing and screening will be performed) and the laboratory of [name] in the department of human physiology at the University of Oregon: An AED, a spare AED battery and spare AED pads, bottled oxygen and face masks. A standard first aid kit is also available.

Emergency Procedures: According to American Heart guidelines, in the event of an adverse cardiopulmonary event, we will begin CPR, and call 211 in Croatia (which is equivalent to calling 911 in the US) and 911 for studies done in the US and will continue CPR as required until emergency medical personnel arrive.

Safety Monitoring: Subjects will be given clear instructions that they should notify the investigators immediately if they experience any of the above-mentioned risk symptoms. During all procedures, all subjects will be non-invasively and continuously monitored for vital signs using: 1) a 3 lead EKG to monitor electrical activity of the heart, and 2) a forehead probe to monitor arterial oxygen saturation and heart rate. During all other procedures subjects will be visually monitored for any signs of discomfort, distress or problems. Throughout all procedures, the investigators will continuously ask the subjects how they are feeling and how they are doing. During SCUBA dives, subjects will be accompanied by a 'dive buddy', a SCUBA-certified diver of similar or greater experience and able to assist the subject in the event of an emergency as is standard for the community.

H. Potential Benefits of the Research

This study will not improve the health of subjects and is only being done to gather information. This study will not improve the health of the general subject population. Completing the aims of this study will have the benefit of contributing to generalizable knowledge.

I. Investigator Experience

The PI and colleagues have been performing cardiopulmonary and respiratory physiology investigations at rest and during exercise in healthy and diseased populations at the University of Oregon for ~12 years. [name] has been performing cardiopulmonary and diving physiology research for >25 years. Other investigators are all well qualified to work with human subjects having done so for many years in both laboratory and field settings. [name] CV is on file. [name] is an internationally recognized expert on diving physiology and his CV is included.

The PIs train all graduate, undergraduate and technical personnel on all laboratory procedures and protocols. Ultrasound technicians, have worked with [name] and [name]'s groups for years and have performed thousands of resting and stress echoes in patients and research subjects.

[name] & [name] will work to ensure that all investigators are cross trained on what is required for human subject research at each individual institution so that all procedures and activities are compliant with the rules and regulations for all institutions involved.

[name] and his team are native Croatian speakers, as well as being fluent English speakers. This will allow for all study procedures, data handling procedures, and informed consent to be explained in either language depending on subject preference. Further, this will allow any important information, such as safety information, to be conveyed to subjects in the language they are most comfortable in. All Croatian collaborators are fluent in both English and Croatian and in some cases, Serbian and other languages. Thus, there will be no problem for our Croatian collaborators to completely understand each respective country's

ethical research practices and requirements. Because our Croatian collaborators will be fully informed of these practices and requirements, and because they all have PhDs, MDs and/or MD/PhDs, they will have absolutely no problem conveying the required information to any of the subjects.

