- c. Subjects with the highest pulmonary arterial pressures will have the greatest restoration of right heart function with sildenafil treatment.

Click here to enter text.

C. Methods, Materials and Analysis

This study will be performed over summers 2019 and 2022 in Split Croatia and the Cardiopulmonary and Respiratory Physiology lab at the University of Oregon in Eugene, Oregon for research activities involving breath hold diving and SCUBA diving subjects. We will perform research activities in breath hold divers and age and sex-matched breath hold diver controls while in Split Croatia. In Eugene, OR we will only perform research activities in age, PFO, and sex-matched breath hold diver controls. SCUBA diving studies will only be performed in Croatia. My lab has extensive experience examining IPAVAL and PFO blood flow as well as measuring pulmonary artery pressure under various environmental challenges such as during exercise, pre- and post-diving and high altitude. We will use saline contrast echocardiography to detect and differentiate between blood flow through IPAVAL and PFO, as we have many times before. We will use Doppler ultrasound as before to quantify differences in pulmonary artery pressure with and without the use of sildenafil. We will use the Journal of American Society for Echocardiography recommendations for making right and left heart function measures as before. We will collaborate with Professor [name], MD, PhD who has extensive experience working with professional, elite, world-record level, breath-hold divers and SCUBA divers. He also has the required laboratory space and resources for performing these experiments at the University of Split Medical School, Split Croatia. There are many elite breath-hold divers that live in Croatia and [name] has established an excellent rapport with the divers and their coach [name] who is with the Faculty of Kinesiology at the University of Zagreb, Croatia. Additionally, [name] has also established an excellent rapport with the Croatian Military for the SCUBA diving studies to be performed using highly experienced divers on a Croatian Navy Base field site that has the required laboratory space and resources for performing the proposed studies. [name] has significant experience working with these groups so it will prevent the possibility of any cultural or political issues interfering with this work. Additionally, [name] and I have worked together before on several projects, see [name] CV for verification as needed.

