
Briefly we will use a single-blind, placebo-controlled study to determine the impact of sildenafil (50 mg, oral) on IPAVAL and PFO blood flow and right heart function and pulmonary pressures. We will use 40 breath-hold divers (20 PFO+, 20 female), 40 age-matched (within 5 years) breath-hold diver Controls (20 PFO+, 20 female), and 50 (25 PFO+, 25 female) SCUBA divers. Sildenafil will be given before the breath hold in the breath-hold divers but after SCUBA diving to avoid any potential decompression illness complications.

Screening at each study visit: All subjects with child bearing potential will be required to take a urine pregnancy test before each visit begins. A positive test at any time will result in exclusion.

Breath Hold Diving Subjects & Controls (Objectives 1 - 3)

Visit 1 Overview: Subject consent, screening, lung function and anthropometrics. Subjects will ingest either a placebo or sildenafil (50mg, oral), wait an hour for peak effect and then breathe low oxygen and high CO2 gas mixtures that mimic blood gases during a breath hold, during which ultrasound measures of the heart and lungs will be made (~4.5 hrs). Note: Breath hold subjects will breathe lower oxygen concentrations and higher carbon dioxide levels than control subjects but slopes of these responses will still be comparable.

Visit 1 Details:

Subjects will undergo informed consent, fill out a health history questionnaire (~45 min).

Subjects will be comprehensively screened for any cardiac abnormalities. Amount of blood flow travelling through the PFO and IPAVAL will be graded using saline contrast echocardiography while the subject is breathing

room air (PFO and IPAVA blood flow) and breathing 100% O₂ (PFO blood flow only). Pulmonary artery pressure will also be measured using ultrasound. Subjects will undergo an intravenous blood draw. We will take 21 mL (~2 Tablespoons) of IV blood (~1.25 hrs)

Subjects will perform pulmonary function testing. (15min)

The subjects will be instrumented with forehead oxygen saturation monitor, ECG and blood pressure cuffs and baseline ultrasound measures of cardiac output, pulmonary pressure and left and right heart function measures will be made before breath hold (~30 min)

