An intravenous catheter will be placed in the subject used for blood draws and bubble injection. Subjects will sit in the left lateral decubitus position for ultrasound screening. An agitated saline contrast injection will be made while transthoracic saline contrast echocardiography (TTSCE, see below) is performed on the subject to evaluate extent of blood flow through IPAVAL and PFO. This will be repeated while breathing 100% O₂ for 10 minutes. Subject will be asked to perform a Valsalva maneuver while breathing room air and 100% O₂. This maneuver enhances blood flow across the PFO. Multiple saline contrast injections (up to 3) may be performed to verify bubble grades/presence of a PFO. In addition, pulmonary artery pressure and stroke volume will be measured with ultrasound.

- **Pulmonary Function Tests** (Day 1 for Breath Hold and SCUBA divers):

Subjects will perform standard non-invasive spirometry to measure a maximal inspiratory and expiratory flow-volume loop, forced vital capacity (FVC), forced expiratory volume in 1 sec (FEV1), and mid expiratory flow (FEF25-75%). These tests will require the subject to blow in and out of a mouthpiece connected to a computerized flowmeter (pneumotachometer). This is a routine clinical test performed in pulmonary function labs in the United States.

- **Transthoracic Saline Contrast Echocardiography (TTSCE)** (Day 1 & 2 for Breath Hold and SCUBA divers): Echocardiography requires a medical sonographer to place a small probe against the subject's ribcage, which transmits and receives sound waves to produce images that are captured and stored on a computer. Saline contrast is made by manually agitating (mixing) 3-5 ml of sterile saline and 1 ml of air to create a suspension (mixture of liquid and gas) of very small bubbles called microbubbles. This suspension is injected through an IV, which allows us to detect the transpulmonary passage of microbubbles.

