1. Sample Size and Data Analyses: Necessary sample size was determined with our primary outcome variables (Pulmonary artery systolic pressure, saline contrast bubble scores, TNFa levels) using our preliminary data, previously published work and *a priori* power analysis. Using G-Power and information about a physiologically-meaningful effect from published studies (i.e. differences in pulmonary artery systolic pressure by 25%, TNFa level differences between PFO+ and PFO- subjects of 50%, a desired power of 0.80, and alpha (0.05), we determined that n = 8-10 individuals of the same sex for each study group (Breath hold and SCUBA divers) would be sufficient to test our hypotheses, using a repeated measures design. Thus, we are asking to recruit up to 20 male subjects (10 with and 10 w/o PFO); and up to 20 female subjects (10 with and 10 w/o PFO) for the breath hold studies. We are also recruiting up to 20 male and up to 20 female age matched control subjects for the breath-hold studies as our control group., We are also requesting to recruit up to and an additional 25 male subjects (12-13 with and 12-13 w/o PFO); and up to 25 female subjects (12-13 with and 12-13 w/o PFO) for the SCUBA studies, for a grand total of 130 subjects, to account for subject attrition and variability in measures.

Table 1

Inclusion	Exclusion

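### The trial is stated to be single-blind and nobody who scans or reads the ultrasound is masked in the text, so the sildenafil–placebo contrast in pulmonary pressure and right heart function is open to avoidable reading bias

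*Combined protocol and SAP*

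**What the plan says.** The only statement on blinding is in Section C (Methods, Materials and Analysis): "Briefly we will use a single-blind, placebo-controlled study to determine the impact of sildenafil (50 mg, oral"). It does not name the blinded party. Nothing else in the document says who issues the doses, who holds the treatment code, who measures the Doppler traces, who grades the bubbles, or whether any of this is masked to drug or visit. The random subject IDs in Section F code the person, not the treatment.

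On outcomes, Section D.1 lists "our primary outcome variables (Pulmonary artery systolic pressure, saline contrast bubble scores, TNFa levels"). Pressure is an ultrasound measure: "We will use Doppler ultrasound as before to quantify differences in pulmonary artery pressure with and without the use of sildenafil" (Section C). Right heart function is also taken by ultrasound at each visit. Shunt flow "will be graded using saline contrast echocardiography while the subject is breathing" room air and then 100% oxygen; in the visit details this grading belongs to the Visit 1 screening, before any dose. TNFa is an ELISA on stored, de-identified serum.

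On people and recordings, Section G says that "a trained and licensed ultrasonographer will perform echocardiography". The contrast echocardiography item in Section C describes a probe that "transmits and receives sound waves to produce images that are captured and stored on a computer".

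**The concern.** The team has written directional hypotheses in Section B: sildenafil lowers pressure, lowers IPAVA flow in PFO- subjects, and restores right heart function most where pressure is highest. Choosing a Doppler envelope, placing a caliper or grading a contrast loop leaves room for judgement. If the person doing this knows which visit was the sildenafil visit, readings can drift towards the expected result.

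Breath-hold divers and their controls take both treatments, one per visit, so a drift tied to the drug goes straight into each subject's paired difference. It is a systematic error: more subjects make the estimate more precise around the wrong value. What is at stake is the sildenafil main effect on pressure and right heart measures in Objectives 2, 3 and 5, and on bubble score if one is taken after dosing.

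**Working it through.** **1. The plan's own figure.** Section D.1 gives n = 8–10 per sex per study group for a 25% pressure difference, power 0.80, alpha 0.05 and a repeated measures design. It gives no SD or within-subject correlation, so the figure cannot be reproduced. Solving backwards for a two-sided paired t-test:
- n = 8 needs a standardized difference of 1.156, so the SD of the paired difference is 25 / 1.156 = 21.6%.
- n = 10 needs 0.996, so the SD is 25 / 0.996 = 25.1%.

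This only gives a scale. On it, a shift of 0.2 SD is about 0.2 × 21.6 = 4.3% to 0.2 × 25.1 = 5.0% of pressure.

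**2. How a reading shift enters.** Let δ be the true drug effect and b the reading shift tied to knowing the drug. The paired difference (sildenafil minus placebo) has mean δ + b. With δ = 0, a two-sided paired t-test rejects with probability

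P(|T| > t(0.975, n−1)), where T is noncentral t with n−1 degrees of freedom and noncentrality (b/SD) × √n.

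Example, n = 40 and b/SD = 0.2: noncentrality 0.2 × √40 = 1.265, critical value 2.023, rejection probability 23.5%.

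**3. Results.** The shifts are assumptions. The n values come from Sections C and D.1.

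| n | What it stands for | 0.1 SD | 0.2 SD | 0.3 SD |
|---|---|---|---|---|
| 10 | upper end of the per-sex sizing | 5.9% | 8.8% | 13.6% |
| 20 | one PFO stratum, breath-hold divers or controls | 7.1% | 13.6% | 24.7% |
| 25 | one PFO stratum, SCUBA | 7.7% | 16.1% | 30.2% |
| 40 | whole breath-hold or control cohort (ceiling) | 9.5% | 23.5% | 45.7% |
| 50 | whole SCUBA cohort (ceiling) | 10.7% | 28.4% | 54.8% |

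With b = 0 every row returns 5%. The n = 25 and n = 50 rows assume that each SCUBA diver takes both treatments. Section C says so explicitly only for the breath-hold visits.

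**4. Cross-check on another scale.** Take the shift as 5% of pressure and the SD of the paired difference as 24% (both assumed). Then b/SD = 5/24 = 0.208, and the rate at n = 40 is 25%. With an SD of 20% to 28% it is 34% to 20%. This agrees with the table.

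**5. Which contrasts are touched.** Write the mean paired difference as δ₊ + b₊ in PFO+ and δ₋ + b₋ in PFO- subjects. Their difference is (δ₊ − δ₋) + (b₊ − b₋). If the shift is the same in both groups, b₊ − b₋ = 0 and the comparison in hypotheses 2b and 5b is unaffected. The same holds for a diver-versus-control comparison of drug effects. The main effect keeps b in full.

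**The case against.** The strongest objection is that the premise is partly inferred. A reader might conclude that the sonographer or grader knows the drug. The documents do not say this: single-blind usually means that the subject is masked, but Section C names no party. What the text supports is that no masking of the person scanning or reading is stated. That stands, and it is why confidence is medium.

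Four further limits also stand.

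- A reader might take all primary outcomes to be exposed. TNFa is a serum assay. The bubble grading actually described is done before dosing, so knowledge of treatment cannot bias it. Post-dose scoring is only implied, by the stated aim and by the listing of contrast echocardiography on Days 1 and 2. Bubble score is also a grade, so the paired-t illustration does not describe it.
- The n = 40 and n = 50 rates are the pooled case, and recruitment is worded as a maximum. Hypotheses 2a, 2b, 5a and 5b are stated by PFO status, where n is about 20 or 25 and the rates are lower. The bias itself does not shrink with n; only the error rate it produces does.
- A reader might infer that the PFO-by-drug comparison is biased too. A common shift cancels there. Only a shift that differs by PFO status would remain, and the documents give no basis for its size.
- The storage sentence sits in the contrast echocardiography item. It does not confirm that Doppler traces and right heart clips are kept, and no reader or off-line reading step is named.

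**Conclusion.** The concern holds in this form: the plan is stated to be single-blind, no text masks the person who scans or reads the ultrasound, and the sildenafil main effect on Doppler pressure and right heart function, and on any post-dose bubble score, is therefore open to a bias that the plan could largely avoid at the reading step.

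Its size cannot be derived from the documents. Under assumed shifts of 0.1 to 0.3 SD and no true effect, the error rate runs from 7.1% to 24.7% at n=20 and from 9.5% to 45.7% at n=40. These figures show sensitivity and do not estimate what will happen. They rest on a two-sided paired t-test at 0.05, which the plan does not specify beyond repeated measures. Sample size and nominal alpha are unaffected. The trial can run as written, but its ultrasound drug effects would face an avoidable objection. This is a cheap improvement, with medium confidence.

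**What to change.** In Section C, replace the bare single-blind label with wording that does the following:

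1. Names who is masked: subject, sonographer, reader.
2. States that pressure, right heart measures and any bubble score used in the drug comparison are taken from the stored recordings after subject, treatment and visit labels are replaced by random codes. Whoever already does the reading reads them in mixed order, before the treatment code is opened. If that person also scanned live, leave a delay.
3. Confirms that Doppler traces and right heart clips are kept as well as contrast loops.
4. Where existing team roles allow, keeps the treatment code from the person scanning, with access to the code preserved for safety.

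Item 2 can also cover recordings already collected, which matters because the document is dated September 2022 and the study spans summers 2019 and 2022.

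The cost is protocol wording plus some time for recoding and off-line reading, and results are not final on the study day. A reader might suppose that item 4 needs no extra staff. The documents do not show this for work at Split, the Navy base and Eugene, so it is conditional. Coded reading also leaves bias at image acquisition in place if the sonographer knows the treatment. No subject, visit or procedure is added.
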